9.5.1.4.1 PHARMACOKINETIC ASSESSMENTS

Serum E6011 Concentration

Blood samples will be collected for measuring serum E6011 concentrations at the time points specified in the Schedule of Procedures/Assessments ([Section 9.5.2.1, Table 4](#)). Serum E6011 concentrations will be measured at the bioanalytical laboratory using a validated, specific, and selective analytical method. Planned blood volume for these measurements is provided in [Table 5 \(Section 9.5.2.2\)](#). Samples will be handled according to the separately prescribed procedures.

9.5.1.4.2 PHARMACOGENOMIC ASSESSMENTS

Not applicable.

9.5.1.4.3 ASSESSMENTS OF BIOMARKERS

Serum Total FKN Concentration

Blood samples will be collected for measuring serum total FKN concentrations at the time points specified in the Schedule of Procedures/Assessments ([Section 9.5.2.1, Table 4](#)). Planned blood volume for these analyses is provided in [Table 5 \(Section 9.5.2.2\)](#). Samples will be handled according to the separately prescribed procedures. Measurements will be conducted at the biomarker assay laboratory.

Serum Concentrations of RF, Anti-CCP, and MMP-3

Blood samples will be collected for measuring serum concentrations of rheumatoid factor (RF), anticyclic citrullinated peptide (anti-CCP) antibody, and matrix metalloproteinase (MMP)-3 at the time points specified in the Schedule of Procedures/Assessments ([Section 9.5.2.1, Table 4](#)). Planned blood volume for these measurements is provided in [Table 5 \(Section 9.5.2.2\)](#). Samples will be handled according to the separately prescribed procedures. Measurements will be conducted at the biomarker assay laboratory.

Serum Concentrations of Cytokines, LRG1, and Ang2

Blood samples will be collected for measuring serum concentrations of cytokines (granulocyte macrophage colony-stimulating factor [GM-CSF], interferon- γ [IFN- γ], interleukin [IL]-1 β , IL-6, TNF α , etc.), leucine-rich alpha-2 glycoprotein 1 (LRG1), and angiopoietin 2 (Ang2) at the time points specified in the Schedule of Procedures/Assessments ([Section 9.5.2.1, Table 4](#)). Planned blood volume for these measurements is provided in

Table 5 (Section 9.5.2.2). Samples will be handled according to the separately prescribed procedures. Measurements will be conducted at the biomarker assay laboratory.

Serum TRACP-5b Concentration

Blood samples will be collected for measuring serum concentrations of tartrate resistant acid phosphatase (TRACP)-5b at the time points specified in the Schedule of Procedures/Assessments ([Section 9.5.2.1, Table 4](#)). Planned blood volume for these measurements is provided in [Table 5 \(Section 9.5.2.2\)](#). Samples will be handled according to the separately prescribed procedures. Measurements will be conducted at the biomarker assay laboratory.

Measurement of Immunocytes Such as Blood CX3CR1-positive Cells

Blood samples will be collected for measuring immunocytes such as blood CX3CR1-positive cells at the time points specified in the Schedule of Procedures/Assessments ([Section 9.5.2.1, Table 4](#)). Planned blood volume for these measurements is provided in [Table 5 \(Section 9.5.2.2\)](#). Samples will be handled according to the separately prescribed procedures. Measurements will be conducted at the biomarker assay laboratory.

Vectra™ DA

Blood samples will be collected for Vectra™ DA, assay kit for biomarkers including VCAM-1, epidermal growth factor [EGF], vascular endothelial growth factor [VEGF]-A, IL-6, tumor necrosis factor receptor-I [TNF-RI], MMP-1, MMP-3, YKL-40, leptin, resistin, serum amyloid A [SAA], and CRP at the time points specified in the Schedule of Procedures/Assessments ([Section 9.5.2.1, Table 4](#)). Planned blood volume for these measurements is provided in [Table 5 \(Section 9.5.2.2\)](#). Samples will be handled according to the separately prescribed procedures. Measurements will be conducted at the biomarker assay laboratory.

9.5.1.4.4 IMMUNOGENICITY ASSESSMENTS

Serum Anti-E6011 Antibody

Blood samples will be collected for measuring of serum anti-E6011 antibodies at the time points specified in the Schedule of Procedures/Assessments ([Section 9.5.2.1, Table 4](#)). The presence or absence of serum anti-E6011 antibody will be assessed at the immunogenicity assay laboratory using a validated, specific, and selective analytical method. When anti-E6011 antibodies are observed, the neutralization activity and isotypes of the anti-E6011 antibody will be evaluated. Planned blood volume for these measurements is provided in [Table 5 \(Section 9.5.2.2\)](#). Samples will be handled according to the separately prescribed procedures.

9.5.1.5 Safety Assessments

Safety assessments will consist of the following, as specified in the Schedule of Procedures/Assessments ([Section 9.5.2.1, Table 4](#)).

All AEs observed; regular monitoring of clinical laboratory tests (including vasculitis marker tests), vital signs, chest x-ray, standard 12-lead electrocardiograms, physical findings, injection site findings, and neurological findings.

9.5.1.5.1 ADVERSE EVENTS AND EVENTS ASSOCIATED WITH SPECIAL SITUATIONS

An adverse event (AE) is any untoward medical occurrence in a patient or clinical investigation subject administered an investigational product. An AE does not necessarily have a causal relationship with the medicinal product. For this study, the study drugs are E6011 and placebo.

The criteria for identifying AEs in this study are:

- Any unfavorable and unintended sign (including an abnormal laboratory finding), symptom, or disease temporally associated with the use of an investigational product, whether or not considered related to the investigational product (Note: Every sign or symptom should not be listed as a separate AE if the applicable disease [diagnosis] is being reported as an AE)
- Any new disease or exacerbation of an existing disease
- Any deterioration in nonprotocol-required measurements of a laboratory value or other clinical test (eg, ECG or x-ray) that results in symptoms, a change in treatment, or discontinuation of study drug
- Recurrence of an intermittent medical condition (eg, headache) not present pretreatment (Baseline)
- An abnormal laboratory test result should be considered an AE if the identified laboratory abnormality leads to any type of intervention, withdrawal of study drug, or withholding of study drug, whether prescribed in the protocol or not

However, worsening of the primary disease (RA) is not considered an AE unless the symptom aggravated unexpectedly (slight change of RA condition is captured under efficacy assessments as disease progression rather than as an AE).

It is the responsibility of the investigator to review all laboratory findings in all subjects and determine if they constitute an AE.

All AEs observed during the study will be reported on the CRF. All AEs, regardless of relationship to study drug or procedure, must be collected during the time the subject signed the informed consent and 70 days after the subject's last dose. Subjects who failed screening in Screening or Observation Phase primarily due to AE(s), such AE(s) and seriousness must be recorded in the CRF.

Any laboratory abnormality considered to constitute an AE will be reported on the CRF. Abnormal laboratory values are listed as separate AEs if they are considered to be part of the clinical syndrome that is being reported as an AE. Medical and scientific judgment is exercised in deciding whether an isolated laboratory abnormality is classified as an AE.

All AEs must be followed for 70 days after the subject's last dose, or until resolution, whichever comes first. However, all SAEs must be followed until resolution or, if resolution is unlikely, to stabilization.

Every effort must be made by the investigator to categorize each AE according to its severity and its relationship to the study treatment.

Assessing Severity of Adverse Events

Adverse events will be graded on a 5-point scale according to Common Terminology Criteria for Adverse Event (CTCAE v4.0). Investigators will report CTCAE grades for all AEs for increasing severity.

As to ALP and γ -GTP, criteria for Grade 2 will be changed from $ULN \times 2.5$ (in the CTCAE) to $ULN \times 3.0$.

Assessing Relationship to Study Treatment

Items to be considered when assessing the relationship of an AE to the study treatment are:

- Temporal relationship of the onset of the event to the initiation of the study treatment
- The course of the event, especially the effect of discontinuation of study treatment or reintroduction of study treatment, as applicable
- Whether the event is known to be associated with the study treatment or with other similar treatments
- The presence of risk factors in the study subject known to increase the occurrence of the event
- The presence of nonstudy, treatment-related factors that are known to be associated with the occurrence of the event

Classification of Causality

Not related	A causal relationship between the study drug and the AE is not a reasonable possibility.
Related	A causal relationship between the study drug and the AE is a reasonable possibility.

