9.3.3 Removal of Subjects From Therapy or Assessment

The investigator or subinvestigator may withdraw the subject from the study at any time for safety or administrative reasons. The subject may stop study drug or withdraw from the study at any time for any reason.

All subjects who discontinue the study should be followed for procedures/assessments at discontinuation as specified in the Schedule of Procedures/Assessments ([Section 9.5.2.1, Table 4](#); also see [Section 9.5.5](#) “Completion/Discontinuation of Subjects” for more information).

A subject will be withdrawn from the study under any of the following circumstances.

1. Occurrence of AE that made it difficult to continue the study
2. Subject is pregnant.
3. Subject's ineligibility is confirmed.
4. Concomitant medication or therapy cannot be continued in accordance with the protocol.
5. Required surgical operation on arthritic disorder
6. Diagnosed with malignant tumor
7. Tested positive in tuberculosis test (QuantiFERON TB® Gold Test or T-SPOT®.TB Test)
8. Tested positive for any of the following: HIV, HBs antigen, HBV DNA, HCV antibody, HTLV-1 antibody, or syphilis (except if false positive for the syphilis test)
9. When the investigator or subinvestigator judges that efficacy of E6011 is insufficient, after the date Version 6 of the protocol was approved by IRB
10. When the investigator or subinvestigator judges that there are other effective treatment options available besides continuing this study, after the date Version 6 of the protocol was approved by IRB

Withdrawal from the study will be considered if a subject skips 3 consecutive administrations.

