9.5.1.3 Efficacy Assessments

After the date Version 6 of the protocol is approved by IRB, it is unnecessary to conduct assessments for efficacy.

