9.5.1.5.2 SERIOUS ADVERSE EVENTS AND EVENTS ASSOCIATED WITH SPECIAL SITUATIONS

A serious adverse event (SAE) is any untoward medical occurrence that at any dose:

- Results in death
- Is life-threatening (ie, the subject was at immediate risk of death from the adverse event as it occurred; this does not include an event that, had it occurred in a more severe form or was allowed to continue, might have caused death)
- Requires inpatient hospitalization or prolongation of existing hospitalization
- Results in persistent or significant disability/incapacity

- Is a congenital anomaly/birth defect (in the child of a subject who was exposed to the study drug)

Other important medical events that may not be immediately life-threatening or result in death or hospitalization but, when based on appropriate medical judgment, may jeopardize the subject or may require intervention to prevent one of the outcomes in the definition of SAE listed above should also be considered SAEs. Medical and scientific judgment should be exercised in deciding whether expedited reporting is appropriate in such situations.

In addition to the above, events associated with special situations include pregnancy or exposure to study drug through breastfeeding; AEs associated with study drug overdose, misuse, abuse, or medication error. These events associated with special situations are to be captured using the SAE procedures (see [Section 9.5.4.2](#) and [Section 9.5.4.3](#)) but are to be considered as SAEs only if they meet one of the above criteria. All AEs associated with special situations are to be reported on the CRF whether or not they meet the criteria for SAEs.

All SAEs must be followed to resolution or, if resolution is unlikely, to stabilization.

The following hospitalizations are not considered to be SAEs because there is no “adverse event” (ie, there is no untoward medical occurrence) associated with the hospitalization:

- Hospitalizations for respite care
- Planned hospitalizations required by the protocol
- Hospitalization planned before informed consent (where the condition requiring the hospitalization has not changed after study drug administration)
- Hospitalization for administration of study drug or insertion of access for administration of study drug
- Hospitalization for routine maintenance of a device (eg, battery replacement) that is in place before study entry

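### The exclusion of RA worsening from adverse events has no exception for serious worsening, so Protocol 9.5.1.5.1 and 9.5.1.5.2 disagree on a serious flare judged not unexpected

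*Protocol*

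**What the plan says.** Protocol 9.5.1.5.1 includes among its AE criteria "Any new disease or exacerbation of an existing disease". It then makes an exception for the disease under study: "worsening of the primary disease (RA) is not considered an AE unless the symptom aggravated unexpectedly". The reason, given in brackets, is that "slight change of RA condition is captured under efficacy assessments as disease progression rather than as an AE". The protocol does not say what counts as unexpected, and the exception does not mention seriousness.

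Protocol 9.5.1.5.2 opens with "A serious adverse event (SAE) is any untoward medical occurrence that at any dose" and lists the outcomes that make it serious. One is "Requires inpatient hospitalization or prolongation of existing hospitalization"; another is lasting or significant disability. The section closes with five kinds of admission that are not SAEs: respite care, admissions that the protocol requires, admissions planned before consent for an unchanged condition, admissions to give study drug or place access for it, and routine device maintenance. RA worsening is not among them.

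Protocol 9.5.4.1 requires every SAE, whatever its cause, to be reported within 1 business day of the investigator learning of it. Protocol 9.7.1.8.2 and SAP 5.6.2 restrict the summary tables to treatment-emergent AEs, with serious TEAEs tabulated in the SAP as a subset.

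Protocol 9.5.1.3 adds: "After the date Version 6 of the protocol is approved by IRB, it is unnecessary to conduct assessments for efficacy". Section 9.5.1.5.1 was not changed to match.

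**The concern.** Whether worsening is unexpected and whether it is serious are separate questions. These subjects have active RA despite methotrexate, and some receive placebo for 24 weeks. An investigator can reasonably regard a flare as foreseeable even when it puts the subject in hospital. Under 9.5.1.5.1 that flare is not an AE; under 9.5.1.5.2 it is an SAE.

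Safety and tolerability is a primary objective. If the event is ruled not an AE, it is absent from the TEAE and serious-TEAE tables and may miss the expedited report. Two sites could handle the same event differently, and both could point to the protocol.

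**Working it through.** The plan has no figure of its own here to reproduce. The check is a comparison of the two sections, followed by two short calculations.

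**Step 1. Apply both rules to each kind of RA worsening.**

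| RA worsening | 9.5.1.5.1 | 9.5.1.5.2 | Consistent? |
|---|---|---|---|
| Unexpected, not serious | AE | Not an SAE | Yes |
| Unexpected, serious | AE | SAE | Yes |
| Not unexpected, not serious | Not an AE | Not an SAE | Yes |
| Not unexpected, serious | Not an AE | SAE | **No** |

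The conflict is confined to the last row. How many events fall there depends on a word that the protocol leaves undefined.

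**Step 2. Look for text that settles the last row.** Both definitions start from an untoward medical occurrence. Section 9.5.1.5.2 does not say whether the RA exclusion carries over to SAEs. It explains its five exempt admissions by the absence of an adverse event, which lets a reader argue that something ruled not an AE cannot be an SAE. The hospitalization criterion and the closed list of exemptions support the opposite argument. Nothing in the text decides between them.

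**Step 3. Test the stated reason.** The bracketed reason concerns slight changes. The efficacy assessments in 9.5.1.3 are joint counts, VAS, HAQ, ESR, CRP and joint x-ray. None of them records an admission or a disability outcome, so the reason does not reach serious worsening at any time in the study.

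**Step 4. Bound the period after Version 6.** Section 7 says the last subject entered the Extension Phase, at Week 24, in March 2018. Version 6 is dated 25 March 2019, about 52 weeks later.

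- Position of the last subjects: 24 + 52 = about Week 76.
- Time remaining: 104 − 76 = about 28 weeks.
- Counting instead from Week 84, where SAP section 3 ends the efficacy analyses: 104 − 84 = 20 weeks.

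The trigger is IRB approval, whose dates are not given. Later approval shortens the gap, and subjects enrolled earlier have less time left. About 28 weeks is therefore an upper figure. All of it is open-label.

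**Step 5. Weight of one event.** With the planned arm sizes, 1/50 = 2.0 percentage points in the 200 mg, 400 mg or placebo arm, and 1/25 = 4.0 points in the 100 mg arm. This is the weight of a single event in an incidence table. It does not estimate how many events are affected.

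**The case against.** The best defence is that the sections can be read together. A flare bad enough for admission may well have aggravated unexpectedly, and is then an AE and an SAE without any conflict. The bracketed reason shows that the exclusion was meant for slight changes. The SAE definition starts from any untoward occurrence, not from events that survive the RA clause. Keeping RA activity out of AE counts while it is measured as efficacy, at Weeks 2, 4, 8, 12, 16, 20 and 24 of the Treatment Phase, is a deliberate and explained choice.

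Much of this stands. The conflict is conditional, and the protocol's likely intention is to capture serious worsening. But the operative sentence turns on whether worsening was unexpected, not on whether it was more than slight, and an investigator who reads it literally may leave a serious event off the AE page.

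Two stronger readings are tempting, and the documents do not support them.

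- *A joint operation is not an AE.* A reader might infer this because 9.3.3 lists "Required surgical operation on arthritic disorder" as a reason for withdrawal. Section 9.5.1.5.1 does not mention surgery, an admission planned before consent for an unchanged condition is expressly exempt from SAE status, and planned surgery during the study is exclusion criterion 33.
- *After Version 6, RA worsening goes almost unrecorded.* Concomitant therapy is no longer entered in the CRF (9.4.7.1.2) and the efficacy measures stop. But reasons for dose change (11.5), reasons for discontinuation, including disease progression and inadequate effect (9.5.5), CRP within safety chemistry (Table 3), physical findings (Table 4) and AE/SAE reporting all continue.

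**Conclusion.** The point holds in a limited form. For RA worsening that is serious but judged not unexpected, one section says it is not an AE and the next makes it an SAE reportable within 1 business day. The two must be reconciled. In the late open-label extension the exclusion also loses its stated basis, for at most about 28 weeks in the last subjects enrolled.

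The conclusion rests on one assumption: that an investigator may regard a serious flare as not unexpected. The documents neither rule this out nor show how often it happened.

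A reader might go further and infer that the randomised safety comparison with placebo is distorted. The documents do not support that. The Version 6 gap opens about a year after the last subject left the placebo-controlled phase. The wording conflict does apply in Weeks 0 to 24, but the number of affected events and their split between arms are unknown. Losing events on placebo would make E6011 look relatively worse, and losing them on E6011 would do the opposite, so neither direction nor size can be stated. The safety analyses are descriptive, so no hypothesis test is at risk.

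This should be corrected, because serious events can be lost under a primary safety objective and the remedy is small.

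**What to change.** Amend Protocol 9.5.1.5.1 so that the exclusion covers non-serious worsening only, and state there that RA worsening meeting any criterion in 9.5.1.5.2 is recorded as an AE and reported as an SAE. With that sentence in place, the undefined test of expectedness no longer decides the handling of serious events. Add a note that, after IRB approval of Version 6, the exclusion can no longer rest on capture by efficacy assessments. Carry the same wording into the CRF completion guideline.

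The cost is a sentence or two of text and a few more SAE reports. The change concerns reporting only and sets no rule for treatment.

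Two further changes are not needed. A separate AE trigger after Version 6 for worsening that leads to a dose change or withdrawal would partly duplicate reasons already collected in the CRF. TEAE and SAE totals with and without RA terms would add little, because SAP 5.6.2 already tabulates by preferred term and lists all AEs and SAEs.

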9.5.1.5.3 LABORATORY MEASUREMENTS

Clinical laboratory tests to be performed, including hematology, chemistry, and urinalysis, are summarized in [Table 3](#). The Schedule of Procedures/Assessments ([Section 9.5.2.1](#), [Table 4](#)) shows the visits and time points at which blood for clinical laboratory tests and urine for urinalysis will be collected in the study.

Table 3 Clinical Laboratory Tests

Category	Parameters
Hematology	WBC count, RBC count, hemoglobin, hematocrit, platelets, and differential of WBC (basophils, eosinophils, lymphocytes, monocytes, neutrophils)
Blood chemistry	
Liver function tests	Total bilirubin, aspartate aminotransferase, alanine aminotransferase, alkaline phosphatase, gamma glutamyl transpeptidase
Renal function tests	Blood urea nitrogen, creatinine
Other	Glucose, HbA1c, albumin, total cholesterol, HDL cholesterol, LDL cholesterol, triglycerides, amylase, inorganic phosphorus, LDH, creatine kinase, total protein, uric acid, sodium, potassium, chloride, calcium, CRP, KL-6, β -D-glucan
Urinalysis	pH, protein, glucose, urobilinogen, ketones, occult blood, specific gravity, amylase
Other	
Vasculitis marker	Serum complement titer (CH50), soluble intercellular adhesion molecule (ICAM)-1, soluble vascular cell adhesion molecule (VCAM)-1, soluble E-selectin, thrombomodulin, D-dimer
Autoantibody	Antinuclear antibody, anti-DNA antibody

CRP = C-reactive protein, HDL cholesterol = high-density lipoprotein cholesterol, LDH = lactate dehydrogenase, LDL cholesterol = low-density lipoprotein cholesterol, RBC = red blood cell, WBC = white blood cell

A laboratory abnormality may meet the criteria to qualify as an AE as described in this protocol (see [Section 9.5.1.5.1](#)) and the CRF Completion Guidelines. In these instances, the AE corresponding to the laboratory abnormality will be recorded in the CRF.

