5.6.2 Adverse Events

The AE verbatim descriptions (investigator terms from the CRF) will be classified into standardized medical terminology using the Medical Dictionary for Regulatory Activities (MedDRA). Adverse events will be coded to the MedDRA (Version 19.1 or higher) lower level term (LLT) closest to the verbatim term. The linked MedDRA preferred term (PT) and primary system organ class (SOC) are also captured in the database. A treatment-emergent adverse event (TEAE) is defined as an AE that emerges during treatment, having been absent at pretreatment (Baseline) or

- Reemerges during treatment, having been present at pretreatment (Baseline) but stopped before treatment, or
- Worsens in severity during treatment relative to the pretreatment state, when the AE is continuous.

Only those AEs that are treatment-emergent will be included in summary tables.

A subject will be counted only once within an SOC and PT, even if the subject experienced more than 1 TEAE within a specific SOC and PT.

The TEAEs will be summarized by treatment group and E6011 overall. The incidence of follow TEAEs will be reported as the number (percentage) of subjects with TEAEs by SOC and PT:

- TEAEs
- TEAEs by maximum intensity
- Serious TEAEs
- TEAEs leading to study drug withdrawn
- TEAEs leading to interruption of study drug
- TEAEs leading to reduction from study drug
- Treatment Related, TEAEs
- Treatment Related, TEAEs by maximum grade
- Treatment Related, Serious TEAEs
- Treatment Related, TEAEs leading to study drug withdrawn
- Treatment Related, TEAEs leading to interruption of study drug
- Treatment Related, TEAEs leading to reduction from study drug

In the analysis, the AEs emerged until 70 days after the last dose are intended

Subject data listings of All AEs, SAEs, AEs leading to death, leading to study drug withdrawn or leading to interruption from study drug will be provided.

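### Protocol Section 9.5.1.5.1 gives opposite instructions on whether a laboratory abnormality belonging to a reported syndrome is a separate adverse event

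*Protocol*

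**What the plan says.** Protocol Section 9.5.1.5.1 lists criteria for identifying AEs. The first begins "Any unfavorable and unintended sign (including an abnormal laboratory finding), symptom, or disease" and carries this note: "Every sign or symptom should not be listed as a separate AE if the applicable disease [diagnosis] is being reported as an AE".

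Later in the section, after stating that a laboratory abnormality judged to be an AE goes on the CRF, the protocol says: "Abnormal laboratory values are listed as separate AEs if they are considered to be part of the clinical syndrome". The syndrome meant is one already entered as an AE. The next sentence deals with the stand-alone case: "Medical and scientific judgment is exercised in deciding whether an isolated laboratory abnormality is classified as an AE".

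Protocol Section 9.5.1.5.3 adds only "A laboratory abnormality may meet the criteria to qualify as an AE as described in this protocol", with a pointer back to Section 9.5.1.5.1 and to the CRF Completion Guidelines.

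Protocol Section 9.7.1.8.2 reports the number and percentage of subjects with TEAEs by SOC and PT. SAP Section 5.6.2 does the same for the Extension Phase. Both use the same counting rule, in the SAP's words: "A subject will be counted only once within an SOC and PT".

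**The concern.** Safety and tolerability is a primary objective (Protocol Section 8.1), and these sentences tell sites how to record the AEs behind the safety tables. For a laboratory finding that belongs to a diagnosis already reported, one sentence says not to list it separately and the other says to list it.

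Two things are at stake. First, a site following the later sentence turns one clinical event into several AE records under different PTs, which the summary tables then show as separate rows. Second, sites that resolve the conflict differently will report the same clinical picture in different ways. Protocol Section 6 plans about 100 sites for 175 subjects, an average of 175 / 100 = 1.75 subjects per site. Section 9.4.3 does not list site as an allocation factor, so nothing in the allocation deliberately balances site conventions across groups.

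**Working it through.** The documents give no figure to reproduce. The check compares the texts and follows the counting rule through to the tables.

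**Step 1. Do the two sentences cover the same case?** Yes. The note concerns signs and symptoms of a diagnosis reported as an AE, and the criterion that carries it counts an abnormal laboratory finding as a sign. The later sentence concerns abnormal laboratory values that are part of a syndrome reported as an AE.

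**Step 2. Do they give the same instruction?** No.

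- Note to the first criterion: diagnosis reported, so the sign is not listed separately.
- Later sentence: syndrome reported, so the laboratory value is listed separately.

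The sentence on isolated abnormalities points the same way. Read literally, a laboratory value already explained by a reported syndrome gets its own record, while one with no other explanation is left to judgment. That inversion suggests a dropped *not*. This is an inference, not something the documents state.

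**Step 3. Does other text settle it?**

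- The fifth criterion in Section 9.5.1.5.1 (an abnormality leading to intervention, or to withdrawal or withholding of study drug) decides whether a laboratory result is an AE. It does not say whether the result is listed beside its diagnosis.
- Section 9.5.1.5.3 refers back without correcting the rule.
- Section 9.6.1 requires CRF entries to follow the CRF Completion Guidelines, which are not among the documents.
- The amendment overviews do not touch the sentence, so it is current text.

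**Step 4. Effect on the tables.** Take one diagnosis with k accompanying laboratory abnormalities, each coded to its own PT.

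- Under the note: 1 record, 1 PT row.
- Under the later sentence: 1 + k records and up to 1 + k PT rows. For illustration, k = 3 gives 1 + 3 = 4 instead of 1.

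The counting rule removes repeats within one SOC and PT only, so a diagnosis term and its laboratory terms stay as separate rows. If a laboratory term falls in a different SOC, the subject also enters that SOC row. The extra rows carry into the treatment-related tables by SOC and PT, and into the by-grade tables that are broken down by PT.

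**Step 5. Size of one extra row.** With planned groups of 25 (100 mg) and 50 (each of the others), one subject moves a PT percentage by 1 / 25 = 4 points at 100 mg and by 1 / 50 = 2 points elsewhere.

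**Step 6. What does not change.**

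- Subjects with any TEAE: the same under both rules, provided the diagnosis is itself a TEAE.
- Subjects with any related TEAE: changes only if a laboratory sign is judged related and the subject has no other related TEAE, so the diagnosis itself must have been judged not related.
- Overall highest grade: changes only if a laboratory sign is graded higher than the diagnosis.

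**The case against.** The strongest reply is that the sentence is a visible slip which many sites would have corrected from context, and that the CRF Completion Guidelines may have given the right rule. All sites are in Japan and non-English pages were removed from the file, so sites may also have worked from a different wording. This stands as a limit on what can be concluded. A reader might infer that events in this trial were in fact counted several times. The documents do not support that, because they do not show which sentence sites followed.

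The note could also be read softly, as meaning that not every sign needs its own record. That narrows the conflict but does not remove it, because the later sentence still directs what the note discourages.

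A reader might further infer biased comparisons between groups. The documents give no evident reason for that in the Treatment Phase: site staff are blinded (Protocol Section 9.4.6), all groups share the same wording, and the safety summaries are descriptive. The placebo-controlled tables rest on Protocol Section 9.7.1.8.2. The SAP supplied covers the Extension Phase, in which all subjects receive E6011.

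Laboratory safety does not depend on AE entry alone either. Measured values are summarised with shift tables (Protocol Section 9.7.1.8.3), and SAP Section 5.6.3 adds markedly abnormal values and box plots. This softens the consequence, but it also means that duplicate laboratory AE rows add little information.

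Finally, it would be too strong to say that entries could not be put right. Protocol Sections 11.3 and 11.4 provide for review of CRFs against source and for audit-trailed corrections.

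**Conclusion.** The point holds as a contradiction in an operative recording rule: the protocol is wrong as written, and nothing in the documents resolves it. Where the later sentence was followed, one event yields 1 + k records and up to 1 + k PT rows, plus SOC rows where the laboratory term lies in another SOC. This assumes that each laboratory sign is coded to its own PT.

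The effect lies in the PT and SOC rows, including those of the related tables and the by-grade tables by PT. It does not extend to a general inflation of AE incidence, because the tables count subjects. The headline any-TEAE, related and highest-grade counts stay put except in the special cases set out above. How often a reported diagnosis has accompanying laboratory signs is not in the documents, so the total effect cannot be sized. The correction is worth making because it is specific and cheap and concerns a primary objective.

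**What to change.** 1. In the last paragraph on AE recording in Protocol Section 9.5.1.5.1, insert *not* after *are*, so that abnormal laboratory values belonging to a syndrome already reported are not listed as separate AEs. This matches the note to the first criterion.
2. Check that the CRF Completion Guidelines give the same rule, and notify sites.
3. For data already collected, a wording change corrects nothing. The planned study period ran to February 2020 and the SAP approval page carries a May 2020 date, so this step matters most. List laboratory-type PTs that coincide with a reported diagnosis in the same subject, query them where possible, and state in the clinical study report which convention was applied.

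The first two steps cost one word, a check of one document and a note to sites. The third costs a targeted listing, any resulting queries and a short statement in the report. No analysis method or sample size changes.
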